1 INTRODUCTION AND BACKGROUND

Over time, the actions of the facial musculature, coupled with loss of skin elasticity and a reduction in subcutaneous tissue, result in the development of facial lines. With the decrease in skin elasticity, repeated facial expressions can become permanent lines¹. The periorbital area is one of the first places on the face to show signs of aging, in the form of lateral canthal lines or Crow's Feet. Genetic differences and environmental toxins, predominantly ultraviolet light exposure and cigarette smoking, may alter the rate of this normal aging process².

Over the past two decades, there has been increasing demand for aesthetic procedures to reverse the effects of aging, particularly in the facial area, and treatment of Crow's Feet is among the most frequent of corrective treatment requests. A number of techniques have been developed to meet the increasing demand for aesthetic procedures to reverse the signs of aging. These include: incisional and excisional surgery, various resurfacing procedures, and the use of temporary or semi-permanent, injectable dermal fillers such as allogeneic or xenogeneic collagen, hyaluronic acid, and autologous fat cells. Topical agents, such as retinoic acids, glycolic acids and lactic acids, are other common methods to minimize Crow's Feet and other facial wrinkles.

Injection of *botulinum* toxin type A (BoNTA) is now one of the most common aesthetic procedures performed and there is a considerable body of medical literature demonstrating its safety and efficacy in aesthetic indications³. On a molecular level, *botulinum* toxin prevents the release of preformed mediators, such as acetylcholine, from motor nerve endings leading to a flaccid paralysis.

BoNTA is an effective treatment for Crow's Feet and is associated with high subject satisfaction. However, the treatment requires multiple injections into a well innervated, sensitive area that is prone to bleeding and bruising and close to delicate organs such as the eyes and lachrymal glands. In addition, misplacement of injection can lead to unwanted effects in non-target areas. Therefore, a topical dermatological formulation to deliver the active ingredient, avoiding the discomforts and potential side effects of injections, would be highly desirable.

Several studies have been conducted assessing the dose-response of the topical *botulinum* product, ET-01⁴, in the treatment of Crow's Feet. The product was well tolerated. This current clinical trial seeks to expand on the existing work.

¹ Ascher, B et al. *Dermatol Surg* 35:1478-1486, 2009

² Carruthers, A et. al. *Dermatol Surg* 2008; 34:S173–S178

³ Coté, T. et al. *J. Am. Acad. Dermatol.* 2005;53:407-15

⁴ ET-01 was previously studied under Anterios' code ANT-1207 and ANT-1401

2 STUDY OBJECTIVES AND PURPOSE

In a previous study ET-01 was applied at doses of up to 1,150 U after skin pre-conditioning with microneedle arrays of the type AdminStamp. The purpose of this Phase 2 study is to repeat the prior study using a different device for skin pre-conditioning, i.e. a Dermaroller.

3 STUDY DESIGN

3.1 Overall Design

The study will be an out-patient, prospectively randomized, double-blind, vehicle-controlled, two-armed, overlapping, sequential ascending dose group, multi-center clinical trial. Each cohort will be fully enrolled and complete the Week 4 visit to allow for a safety review before initiating enrollment of the next dose group.

3.2 Treatment Groups / Sample Size

The following dose groups and sample sizes are planned:

Dose Group		Vehicle	690 U	1,100 U	Σ Total
Cohort 1	N =	12	24		
Cohort 2	N =	12		24	
Total	N=	24	24	24	72

The treatment area will be preconditioned with a Dermaroller MC 905, 0.5 mm. ET-01 will be applied immediately after pre-conditioning.

3.3 Efficacy Parameters and Timing

Efficacy will be assessed using the Crow's Feet Wrinkle Scale (CFW), which is a published validated, photo-numeric guide that grades severity of lateral canthal lines into one of the five categories of 0=none, 1=minimal, 2=mild, 3=moderate, and 4=severe. (see Appendix A for details). Using the same scale, assessments will be made by both, the investigator (IGA) and the subjects (SSA). Assessments are made "static" to avoid recall bias.

The IGA and SSA are recorded separately for the right and left canthal areas, both "at rest" and "on contraction". The IGA and SSA will be recorded at each visit.

3.4 Safety Parameters and Timing

Safety will be assessed during the study by collection of study events, review of concomitant treatments and laboratory data. Clinical adverse event reporting will be conducted at each visit.

All laboratory measurements will be performed by a central laboratory using appropriate and validated methods. Values will be reported to the Investigator and the Sponsor. Laboratory reference range values will be described in the laboratory manual. Investigators will assess all out of range values as being clinically significant or not.

3.4.1 Vital signs

Weight, height (Screening visit only) temperature, resting pulse, blood pressure, and respiration rate. Vital signs will be recorded at every visit.

3.4.2 Muscle Weakness or Paralysis

Participants will be monitored for potential signs of *botulinum* induced muscle weakness or paralysis. Subjects will be evaluated for Signs of Botulinum Toxin Spread (muscle weakness - ocular and the extremities) or difficulty swallowing or breathing (cranial nerve assessment, Appendix B).

The neurologic assessments are made at Baseline, Week 1, 2, and Week 4.

3.4.3 Hematology

Non-fasting clinical hematology evaluations are:

hemoglobin, hematocrit, red blood cell count, white blood cell count, with a differential, and a platelet count.

Non-fasting clinical hematology evaluations will be performed at Week 0 (Baseline), Week 4, and Week 26/End of Study.

3.4.4 Clinical Chemistry

A standard non-fasting chemistry panel will be performed which will include the following parameters:

glucose, uric acid, calcium, sodium, potassium, phosphorus, chloride, alkaline phosphatase, aspartate aminotransferase, alanine aminotransferase, total bilirubin, bicarbonate, creatinine, blood urea nitrogen, lactate dehydrogenase, total protein, albumin.

The chemistry panel will be performed at Baseline (Week 0), Week 4, and Week 26/End of Study. A urine pregnancy test will be performed for women of child-bearing potential at Baseline and the Week 4 visit.

3.4.5 ECG Testing

A 12-lead ECG will be recorded measuring the RR, PR, QRS, and QT interval durations prior to treatment application at Baseline and at Week 2.

3.4.6 Immunogenicity

Plasma samples will be banked for future analysis of anti-botulinum serum antibodies as a safety parameter for possible immunization against botulinum.

[figure not shown]
Samples will be taken at Baseline, Week 4, and Week 26.

3.4.7 Photography

Color photographs will be taken at every visit. Five pictures will be taken as described in Appendix C.

3.4.8 Treatment Procedure

To capture the level of comfort or discomfort caused by the skin pre-treatment with the Dermarollers and subsequent rubbing in of the study medication subjects will be asked to rate their experience on a scale from “-5” (very bad) to “+5” (very good).

3.5 Study Visits and Procedures

A schematic study diagram is shown below:

Procedure	Scr./BL	W 1	W 2	W 4	W 8	W 12	W 18	W 26	End of Study#
	Day 0 ± 0	Day 7 ± 2	Day 14 ± 3	Day 28 ± 4	Day 56 ± 7	Day 84 ± 7	Day 126 ± 7	Day 182 ± 7	
Informed Consent	X								
Assess Eligibility & Medical History	X								
Review Con-meds	X	X	X	X	X	X	X	X	
Record AEs	X	X	X	X	X	X	X	X	
Weight and Vital Signs	X	X	X	X	X	X	X	X	
Signs of Botulinum Spread	X	X	X	X					
Hematology and Chemistry	X			X					X
Anti-Botulinum Antibodies	X			X					X
Urine Pregnancy test (WOCBP)	X			X					
ECG	X		X						
IGA Score	X	X	X	X	X	X	X	X	
Subject Self-Assessment (SSA)	X	X	X	X	X	X	X	X	
Photography	X	X	X	X	X	X	X	X	
Randomization	X								
Apply Study Medication	X								

also for early termination

The study will consist of up to 8 office visits.

3.6 Measures to Minimize/Avoid Bias

To minimize bias, subjects will be randomly allocated to one of the three treatment groups, i.e. vehicle (group A) vs. low dose (group B) vs. high dose (group C). Neither subjects nor investigators will be aware of the treatment allocation.

4 MEDICATION AND DOSING

4.1 Dose Rationale

Finding evidence of a safe and effective dose is the purpose of this study. In previous clinical studies doses of up to 2,000 U were applied under occlusion and were well tolerated. In study LCL-206 which employed microneedle skin preconditioning, doses of up to 1,150 U were applied safely. In this study, a different microneedle device is used for skin pre-conditioning. In case this may lead to somewhat better relative bio-availability, this study, LCL-208, will start at 690 U or 5/8 of the maximum dose administered in study LCL-206. After a safety review, it is planned to dose escalate by factor 1.6 to 1,100 U, a level just below the maximum dose level of study LCL-206.

4.2 Treatment of Subjects

The study preparation or vehicle consists of a milky, white lotion of low viscosity. The drug product and diluents will be provided in kits containing 3 mL dropper bottles that contain either ET-01 or Vehicle.

The following dose groups and sample sizes are planned:

[figure not shown]
Dose Group		Vehicle	690 U	1,100 U	Σ Total
Cohort 1	N =	12	24		
Cohort 2	N =	12		24	
Total	N=	24	24	24	72

Randomization to a treatment group, i.e. ET-01 or Vehicle, will be obtained following a randomization list prepared by the Sponsor. Allocation to a dose level will be driven by sequence of enrollment.

The study medication will be applied TOPICALLY and only to subject's canthal areas. The site will be instructed to make sure no syringes or needles are present in the treatment room before study medication is brought into the room.

[figure not shown]
The treatment area is the periorbital region in the distribution of the muscles responsible for the Crow's Feet wrinkles. The muscle being treated to reduce the Crow's Feet wrinkle – the *orbicularis oculi* – is illustrated Figure 1.

Figure 1: *M. orbicularis oculi*

In general, the treatment region begins on the bony rim of the orbit, extending laterally to approximately one centimeter from the exterior edge of the hairline, 1 - 1.5 cm above and 1.5 – 2 cm below a horizontal line emanating from the lateral canthus to the hairline. This area of application is illustrated by the black outline in the picture below:

Figure 2: Treatment Area

As a guide to treatment, it is helpful to have the subject contract the orbicularis oculi muscle by asking the subject to produce a maximal smile so that the muscular extension can be visualized for that subject's treatment. In no case, however, should ET-01 ever be applied within the area circumscribed by the interior edge of the orbital rim.

The clinical investigator will wipe the periorbital region with an alcohol wipe and then dry thoroughly with a cotton swab. The treatment area will be pre-conditioned by pressing the Dermaroller firmly, applying approximately 2-3 pounds of pressure, to the skin. The location of the area of pre-conditioning are illustrated by the white outline in Figure 2. There will be ten (10) rolls made along the bony rim of the orbital cavity in an up-and-down motion. After each roll of the Dermaroller, the Dermaroller will be lifted off the skin. The first roll will start at the area of the skin corresponding to the superior aspect of the outlined white box and then rolled downward. The second roll will start at the area of the skin corresponding to the inferior aspect of the outlined white box - slightly offset from the first roll - and then rolled upward. Thereafter, each roll will start at the area of the skin corresponding to the superior aspect of the outlined white box, followed by a roll that will start at the area of the skin corresponding to the inferior aspect of the outlined white box.

Immediately thereafter, using a gloved finger, the investigator will massage 8 drops of the topical treatment into the skin of the treatment area.

The medication is of low viscosity and administered one drop at a time to avoid run-off. As an additional precaution, the subject will be positioned on an examination table or fully reclined examination chair such that his/her temple will slightly slant backwards and to the side, directing any run-off away from the eyes and into the hairline. The subject will be instructed to close his/her eyes which will then be covered with eye covers, e.g., IPL-Aid™ Disposable Eye Shields, and an absorbent paper or cloth.

There are 3 phases that the study drug will go through before it is completely absorbed into the skin. The clinical investigator will be instructed to make sure to visually observe all 3 phases during application process before additional small aliquots of Test Article are applied as listed below:

Phase 1: Gelling	the sample becomes clear in color and flowable.
Phase 2: Creaming	the sample becomes more viscous, is white in color, and sticky.
Phase 3: Absorption	the sample becomes clear in color and has a glossy smooth finish. There is no visible residue left on the skin after absorption.

The process of treatment application will take at least 10 minutes each and may, in some cases, take up to 15 mins to complete for each periorbital region. After the last drop as been applied to the skin, it is critical that the product is continually rubbed onto the skin until all 3 phases has been observed for the last time, especially the creaming phase. This procedure will be completed when there is no liquid visible on the surface of the skin.

This procedure will be employed for both, the right and left periorbital regions. The start and finish time will be recorded in the eCRF. The study medication kit drug label will be completed and peeled-off for application in the subject's Case Report Form.

4.3 Drug Storage and Drug Accountability

4.3.1 Drug Storage

The investigator will ensure that the investigational product is stored in appropriate conditions in a secure, locked refrigerator with controlled access. Until ready for dispensing, the investigational product will be stored at a controlled temperature of +5°C. Temperature logs will be maintained to document that the storage temperature has not deviated from the recommended range. Should a deviation occur in the storage temperature of unopened investigational product kits, the investigator will complete and submit an Investigational Product Deviation Report form by e-mail or fax to the Sponsor. The Sponsor will review the information submitted and will provide direction regarding further use of the applicable kit/s.

4.3.2 Drug Accountability

The principal investigator at each site is responsible for maintaining accurate records of the receipt and application of all investigational materials. The investigator may apply the investigational drug only to eligible subjects enrolled in the study. All applications of the investigational drug will be conducted at the study sites.

Eirion Therapeutics will provide drug accountability forms to assist the investigator in maintaining current and accurate inventory records covering receipt, application, and the return of investigational drug supplies. When a shipment is received, the investigator or designee will verify the quantities received. The Case Report Form includes the identification of the person to whom the drug is applied, the date of application, and any returned or unused drug. These records will be readily available for inspection by the Sponsor or a monitor and are open to any other regulatory authority inspection at any time.

When the supplies are returned, the investigator, designee, or monitor signs the investigational drug return log to verify that all used, unused, or partially used supplies have been returned, and that no study supplies remain in the investigator's possession. One copy of all inventory records and the return statement are retained by the investigator for the study files.

At study termination, unless otherwise specified, all used, unused, and partially used drug supplies should be returned to the distribution center. The study drug return form will be returned to Eirion Therapeutics, Inc., and a copy will be maintained on site.

5 SELECTION AND WITHDRAWAL OF STUDY SUBJECTS

The study will enroll adult female subjects diagnosed with mild to severe Crow's Feet.

5.1 Inclusion Criteria

- able to understand and give written informed consent
- females 25 - 65 years of age
- willing to have facial pictures taken per protocol
- minimal to moderate Crow's Feet wrinkles (IGA 1-3) at rest
- moderate to severe Crow's Feet (IGA 3-4) on contraction
- moderate to severe Crow's Feet (SSA 3-4) on contraction
- Have adequate vision without the use of eyeglasses to assess facial wrinkles in a mirror (contact lenses are OK)
- willingness to refrain from the use of facial fillers, retinoids, botulinum toxins, laser treatments, or any product affecting skin remodeling or that might cause an active dermal response during the course of the study
- female subjects must have a negative urine pregnancy test and be non-lactating at the Baseline visit
- female subjects of child bearing age must utilize one of the following methods of birth control throughout the study: IUD, diaphragm, a condom, a spermicidal gel or foam, oral contraceptives (provided subject has been utilizing this method for at least 3 months prior to baseline and has not changed the brand within this period), or patch, injectable, implantable, or vaginal ring contraceptives. Subjects may also participate if they are surgically sterilized (tubal sterilization or hysterectomy) or are in menopause.
- subjects should be in good general health as determined by the investigator and free of any disease that may interfere with study evaluations or the Investigational Product

5.2 Exclusion Criteria

- history of adverse reactions to any prior botulinum toxin treatments
- history of vaccination with botulinum toxin
- history of non-response to any prior botulinum toxin treatments
- botulinum toxin treatment in the prior 6 months
- history of periocular surgery, brow lift or related procedures
- soft tissue augmentation or any procedures affecting the lateral canthal region in the prior 12 months
- dermabrasion or laser treatment in the periocular region in the last 6 months
- topical prescription-strength retinoids in the prior 3 months to the treatment area
- application of any topical prescription medication to the treatment area within 14 days prior to treatment
- subjects on clinically significant, concomitant drug therapy (See section 5.3 below).
- present or history of neuromuscular disease, eyelid ptosis, muscle weakness or paralysis
- present or history of “dry eye”
- systemic aminoglycoside use in the week prior to treatment application
- participation in another investigational drug trial or receiving any investigational treatment(s) within 30 days of Baseline
- alcohol or drug abuse within the past 3 years
- female subjects who are pregnant or are nursing a child
- psychiatric disease interfering with the subject’s ability to give informed consent
- refusal or inability to comply with the requirements of the protocol for any reason

5.3 Concomitant Medication

Any prescription or over-the-counter medication taken during the study will be recorded in the appropriate section of the Case Report Form.

The following medications are prohibited:

- Botulinum toxin containing products for the course of the study
- The use of any facial fillers, laser treatments, or any product affecting skin remodeling for the course of the study
- Dermabrasion or laser treatment in the periocular region for the course of the study
- Topical prescription-strength retinoids in the periocular region for the course of the study
- Tanning booths or sun exposure for the treatment day and the following 2 days
- Any topical medications applied to the treatment area for the day of treatment and 5 days following treatment. Toiletry and make-up are permitted.

- Systemic aminoglycosides for the day of treatment and 7 days following the treatment application at the Baseline Visit
- Investigational medications or treatments within 30 days of Baseline and during the course of the study

5.4 Subject Withdrawal or Removal From Study

As stated in the Informed Consent, all subjects reserve the right to withdraw from the study at any time. An effort will be made to determine why a subject discontinues the study prematurely. The reason for study discontinuation will be recorded in the eCRF. All subjects who terminate the study early and have completed the Baseline Visit will be encouraged to complete Week 26/End of Study procedures.

Any subject found to have entered the study in violation of this protocol may be withdrawn from the study after discussion with the sponsor. Any subject who requires the use of an unacceptable concomitant medication may be withdrawn from the study. The investigator will discontinue any subject from the study if, in the investigator's opinion, it is not in the subject's best interest to continue.

If the reason for withdrawal is an AE/ SAE, the specific event will be recorded and every effort will be made by the Investigator to document the outcome. The date that the subject is withdrawn from the study and the reason for discontinuation will be recorded on the Case Report Form. Subjects who discontinue from the study or who are lost to follow up will not be replaced.

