6.1.9 Study Exit / Early Termination

The scheduled Study Exit is at Week 26. However, if a subject should discontinue prematurely, the following will be performed in addition to the procedures scheduled for the patient's terminating visit:

- collect non-fasting blood samples for laboratory safety testing

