7.3 Stopping Rules

The study is designed as a sequential, overlapping cohort, dose-escalation trial. Enrollment will be halted after each cohort until a safety review has been completed.

- Enrollment will be halted in the event that one serious adverse event (SAE), considered to be probably or definitely related to the administration of study medication, is observed.
- Enrollment will be halted in the event that one AE is observed considered to be indicative of distant spread of study medication or unintended exposure to other beings.
- The Sponsor may stop the study in its entirety or discontinue individual study centers at its discretion for any reason or, e.g. if it is observed that the protocol or sound clinical practices are not being followed, or for any other reasons.

The study protocol calls for only one single application of study medication at Baseline (Week 0). Since there is no continuous treatment, no stopping rules for subjects are

applicable and subjects will be encouraged to participate in the study until the scheduled termination visit at Week 26.

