9.1.2 ITT and PP population

Statistical analysis of efficacy will be performed on the ITT population of all treated subjects with at least one post-baseline visit, including those for whom only incomplete data are available.

Where data are missing due to subject discontinuation or other reasons, the last post-baseline observation carried forward (LOCF) procedure will be used for each post-baseline visit with missing data. The exception to this procedure will be the treatment of missing data only on one side of the face, as discussed below. Subjects who are lost to follow-up and who do not have at least one post-baseline visit will not be included in the analysis.

An additional analysis may be performed in the per protocol population. Subjects will be considered “per protocol” if they complete the final visit evaluation without a major protocol violation. No data imputations will be made for this analysis.

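### Scores taken after prohibited botulinum toxin or other periocular treatment have no analysis rule, so by default a fall they cause counts as response to the randomized arm

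*Combined protocol and SAP*

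**What the plan says.** Section 5.3 (Concomitant Medication) lists among the prohibited items "Botulinum toxin containing products for the course of the study". A further entry bars fillers, lasers and skin-remodeling products over the same period, and another names "Topical prescription-strength retinoids in the periocular region for the course of the study". Periocular dermabrasion is likewise ruled out.

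The consequence is in section 5.4: "Any subject who requires the use of an unacceptable concomitant medication may be withdrawn from the study". Nothing there, or elsewhere, says what happens to the scores. Section 7.3 points toward retention: "subjects will be encouraged to participate in the study until the scheduled termination visit at Week 26". For a subject who leaves early, section 6.1.9 adds safety bloods "in addition to the procedures scheduled for the patient's terminating visit", so the IGA and SSA due at that visit are still taken.

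On the analysis side, section 9.1.2 defines the ITT set as "all treated subjects with at least one post-baseline visit, including those for whom only incomplete data are available", and LOCF fills visits where data are missing. A per-protocol analysis is optional and turns on a major protocol violation, which is not defined. Section 9.2.2 defines response as an IGA-C reduction of at least 2 points from baseline. Each dose is compared with vehicle by chi-square at every visit, at two-sided 0.05, with no condition on other treatment received.

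**The concern.** Section 1 describes injected botulinum toxin as effective for Crow's Feet, so this prohibited product acts directly on the primary endpoint. A score observed after an injection is not missing, so LOCF does not displace it. If it is 2 points below baseline, it meets the response definition.

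Withdrawal does not reliably remove the problem. It is discretionary, and a post-injection score taken at the terminating visit is itself an observation that LOCF can carry to later visits.

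Subjects enter with moderate to severe lines on contraction, receive one application and are followed for 26 weeks. Those without benefit plausibly have the most reason to look elsewhere. If they are more numerous on vehicle, the drug-vehicle difference shrinks at visits after use. If the user is in an ET-01 arm, the difference grows. With 24 subjects per arm, single subjects can decide a nominal result. Without a rule set in advance, their handling could be settled after the data are seen.

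**Working it through.** **No figure to reproduce.** Section 9.1.1 says only that the study is powered on interim results of two other studies. It gives no response rate, effect size or power. The main finding is therefore textual, and the arithmetic below only illustrates it.

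**Inputs from the documents:** 24 subjects per arm (section 3.2; vehicle is 12 + 12 across the two cohorts); chi-square test, two-sided alpha 0.05 (section 9.2.2).

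**Assumed inputs, not in the documents:** true response rates of 35% on active and 5% on vehicle; k = 0 to 3 per 24 non-responders taking a prohibited treatment, so uptake u = k/24; and a probability c that such a subject then shows a 2-point fall.

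**Formula.** The counted response rate in an affected arm is p + (1 − p) × c × u. Power is the exact binomial probability that the uncorrected chi-square gives p < 0.05 with 24 v 24.

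- Scenario A: vehicle only, c = 1. At k = 3, vehicle = 0.05 + 0.95 × 3/24 = 16.9%; active stays at 35%.
- Scenario B: same uptake among non-responders in both arms, c = 1. At k = 3, vehicle = 16.9% and active = 0.35 + 0.65 × 3/24 = 43.1%.
- Scenario C: as B, with c = 0.5. At k = 3, vehicle = 0.05 + 0.95 × 0.5 × 3/24 = 10.9% and active = 0.35 + 0.65 × 0.5 × 3/24 = 39.1%.

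| k per 24 | A: vehicle only | B: both arms | C: both arms, half convert |
|---|---|---|---|
| 0 | 81% | 81% | 81% |
| 1 | 63% | 70% | 75% |
| 2 | 45% | 60% | 70% |
| 3 | 31% | 53% | 65% |

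At k = 3 the counted difference falls from 30 points to 35 − 16.9 = 18.1 in A, and to 30 × (1 − 3/24) = 26.25 in B. If only an ET-01 arm were affected, it would rise to 43.1 − 5 = 38.1 points.

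**Without assumed rates.** One extra vehicle responder can move a nominal result across 0.05 (uncorrected chi-square, active v vehicle, 24 per arm):

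- 4 v 0, p = 0.037; 4 v 1, p = 0.156
- 6 v 1, p = 0.041; 6 v 2, p = 0.121
- 8 v 2, p = 0.033; 8 v 3, p = 0.086

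The reverse also holds. With no vehicle responders, four active responders are the fewest that reach p < 0.05, so one contaminated ET-01 subject can supply the fourth.

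**The case against.** The gap is one of silence. No sentence says that post-use scores are to be kept, and section 9.5 promises a separate Statistical Analysis Plan before unblinding that could add a rule. This stands as a limit on the wording: the plan does not direct that such scores be counted, but its general definitions count them by default. No rule appears in the text available.

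There are safeguards. Subjects must be willing to refrain from these products (5.1), those refusing or unable to comply are excluded (5.2), medication is queried at every visit (7.4), and a per-protocol analysis is possible (9.1.2). These should make use less frequent, but none says how to analyse a breach in the primary comparison.

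A reader might infer from scenario A that the plan stands to lose 50 points of power and that the bias always hides an effect. The documents do not support that. The scenario places every case on vehicle and assumes every user responds. At the assumed rates about 16 of 24 active subjects are also non-responders (0.65 × 24 = 15.6), against about 23 on vehicle (0.95 × 24 = 22.8). Equal uptake among them gives the smaller losses in B and C.

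A reader might also infer that filler, laser or retinoid use would produce a 2-point fall. The documents support a clear action on the endpoint only for botulinum toxin.

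Finally, analysing scores as observed whatever treatment follows is a recognised ITT strategy. That is fair: the choice is open, but it needs to be stated in advance.

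**Conclusion.** The concern holds as a missing rule with a definite default. Under sections 9.1.2 and 9.2.2 as written, a 2-point IGA-C fall after prohibited toxin use counts as response in whichever arm it occurs, and optional withdrawal under 5.4 does not prevent this. The likelier direction is toward no difference, on the unproven premise that non-responders seek treatment and are more numerous on vehicle. Inflation of an ET-01 arm is also possible.

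The size cannot be fixed from the documents. At 35% v 5% and three per 24, power drops from 81% to between 31% and 65%, depending on which arms are affected and how many users convert. If nobody uses a prohibited product, nothing changes. What rests on no assumed rate is the fragility: at 24 per arm, one reclassified subject can reverse a nominal result.

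**What to change.** State in 9.1.2/9.2.2, or in the SAP before unblinding:

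- From the first recorded use of botulinum toxin, or of filler, laser, dermabrasion or prescription retinoid in the periocular area, the subject is a non-responder at that and all later visits for IGA-C, SSA-C and the composite.
- For mean change, scores after use are excluded and LOCF carries only the last score before use. Simply setting later scores to missing is not enough, because a post-use score from an earlier visit could otherwise be carried.
- The as-observed analysis is shown as a sensitivity analysis, and affected subjects are listed by arm.
- The existing concomitant-medication query also records these procedures. Sections 5.3 and 6 require medication to be recorded but do not clearly require capture of filler, laser or dermabrasion.

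The cost is one added analysis rule, one sensitivity table and a small extension of an existing query. The downside is that a subject already responding before prohibited use is then counted as a non-responder; the sensitivity analysis shows how much that matters. The rule governs only how scores are analysed and leaves the withdrawal decision in 5.4 as it is.
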